4.3.2.1 Balovaptan

A single dose of balovaptan 10 mg will be administered alone each morning of Days 1 to 10 of Period 1 and in combination with rifampicin on Days 7 to 16 of Period 2, after an overnight fast of at least 8 hours in each period.

4.3.2.2 Rifampicin

A single dose of rifampicin 600 mg will be administered alone on each morning of Days 1 to 6 of Period 2, and in combination with balovaptan on Days 7 to 16 of Period 2. In both periods, the study drugs will be swallowed whole with 240 mL of still water.

Rifampicin should be taken at least 30 minutes prior to or at least 2 hours after a meal.

Therefore, rifampicin alone or in combination with balovaptan will be administered at least 30 minutes prior to breakfast; lunch, dinner, and afternoon/evening snacks will be administered 4 or more hours post dose.

In both periods, the study drugs will be swallowed whole with 240 mL of still water.

4.3.3 Investigational Medicinal Product Accountability

Balovaptan will be provided by the Sponsor where required by local health authority regulations. The study site will acknowledge receipt of IMPs supplied by the Sponsor by returning the appropriate documentation form to confirm the shipment condition and content. Any damaged shipments will be replaced. Rifampicin will be obtained commercially by the site.

The IMPs will either be disposed of at the study site according to the study site's institutional standard operating procedure or be returned to the Sponsor (if supplied by the Sponsor) with the appropriate documentation. The site's method of destroying Sponsor-supplied IMPs must be agreed to by the Sponsor. The site must obtain written authorization from the Sponsor before any Sponsor-supplied IMP is destroyed, and IMP destruction must be documented on the appropriate form.

Accurate records of all IMPs received at, dispensed from, returned to, and disposed of by the study site should be recorded on the Drug Accountability Form and Drug Dispensing Form.

4.4 CONCOMITANT THERAPY, PROHIBITED FOOD, AND ADDITIONAL RESTRICTIONS

Concomitant therapy consists of any medication (e.g., prescription drugs, over-the-counter drugs, vaccines, herbal or homeopathic remedies, nutritional supplements) used by a subject in addition to protocol-mandated treatment from 14 days prior to initiation of study drug to the study completion/discontinuation visit. All such medications should be reported to the Investigator and recorded on the Concomitant Medications eCRF.

4.4.1 Permitted Therapy

Existing hormonal contraceptives and hormone replacement therapy regimens may remain unchanged during the conduct of the study. However, women of childbearing potential must agree to use an alternative highly effective non-hormonal contraception method (e.g., non-hormonal IUD) combined with a barrier method for 90 days after the last dose of study drug.

Acetaminophen/paracetamol is allowed up to a maximum dose of 2 g/day up to 48 hours prior to dosing and during the in-house portion of the study, but total should not exceed 4 g total during the week prior to dosing. Subjects will be instructed not to exceed these limits.

4.4.2 Prohibited Therapy

Any prescribed systemic or topical medication within 4 weeks (or within 5 times the elimination half-life of the medication, whichever is longer) prior to the first study drug administration through the follow-up visit or slow release medicinal formulations considered to still be active within 4 weeks (or within 5 times the elimination half-life of the medication, whichever is longer) prior to the first study drug administration are prohibited through the follow-up visit, unless in the opinion of the Investigator the medication will not interfere with the study procedures or compromise safety. Any non-prescribed systemic or topical medication or herbal remedies are prohibited for 7 days prior to the first study drug administration through follow-up. This is with the exception of medications to treat AEs, unless the rationale for the exception is discussed and clearly documented between the Investigator, the medical and safety monitor and the Roche clinical pharmacologist, and with the exception of permitted therapies per Section 4.4.1. All medication administered to manage AEs should be recorded on the Adverse Event Report Form.

The following concomitant medications in particular are prohibited, unless an exception has been agreed to as mentioned above.

- Any inhibitor of CYP3A taken within 4 weeks (or within 5 half-lives, whichever is longer) prior to study drug administration, including but not limited to the following drugs: ketoconazole, miconazole, itraconazole, fluconazole, erythromycin, clarithromycin, ranitidine, and cimetidine, until follow-up.
- Any inducer of CYP3A taken within 4 weeks (or within 5 half-lives, whichever is longer) prior to study drug administration in Period 1, including but not limited to the following drugs: rifampicin, rifabutin, glucocorticoids, carbamazepine, phenytoin, phenobarbital, and St. John's wort, until follow-up, except for rifampicin in Period 2.
- Investigational drug or medical device therapy (other than protocol-mandated study treatment) is prohibited 90 days prior to first dosing, or within 5 months prior to first dosing in case of a study with a biological, as calculated from the day of follow-up from the previous study of study treatment and during study treatment.

4.4.3 Prohibited Food

- Consumption of methylxanthine-containing products (e.g., coffee, tea, cola, chocolate) will be forbidden from 48 hours prior to dosing and during the stay in the CRU
- It is not permitted to take any nutrients known to modulate cytochrome CYP3A activity (e.g., grapefruit juice; Seville orange) within 2 weeks prior to first dosing until discharge from the CRU at the end of the study.
- Subjects should refrain from consumption of any foods containing poppy seeds within 48 hours (2 days) prior to screening and each admission to the clinical research center to avoid false positive drug screen results.

4.4.4 Additional Restrictions/Considerations

- Subjects should have fasted for at least 4 hours prior to the screening visit, each admission of the CRU, and the follow-up visit.
- Water will be allowed ad libitum until 1 hour prior to dosing and from 1-hour post dosing. The excessive consumption of fluids (greater than 3 liters per day) should be avoided.
- For maximum absorption, rifampicin should be taken at least 30 minutes prior to or at least 2 hours after a meal.
- In each period, study drugs will be administered at least 30 minutes prior to breakfast, after an overnight fast of at least 8 hours. Standardized meals will be served to all subjects at days and the times noted in [Appendix 1](#). On these days a standardized breakfast, lunch, snack, and dinner will be served at similar times of the day (the same meal at each respective meal time), and subjects will be required to complete the meal. The standardized breakfast will be served 30 minutes post dose; standardized lunch, 4 hours post dose; and standardized dinner 10 hours post dose on Day 10 of Period 1, and Days 6 and 16 of Period 2 (post dose is relative to time of dosing of balovaptan alone, rifampicin alone, or balovaptan + rifampicin, as applicable). All other meals will conform to PRA standards. Lunch, dinner, and afternoon/evening snacks will be provided 4 or more hours post dose.

- Between the screening visit and follow-up, alcohol must be restricted to no more than 2 units per day (1 unit of alcohol equals ½ pint (285 mL) of beer or lager, 1 glass (125 mL) of wine, or 1/6 gill (25 mL) of spirits). Alcohol consumption will not be allowed 48 hours before balovaptan dosing and while staying in the CRU. Random alcohol/drugs of abuse testing may be employed throughout the study to verify compliance.
- Use of tobacco will not be permitted 48 hours prior to admission to the clinical unit and until discharge from the CRU in each study period.
- Subjects should refrain from strenuous exercise for at least 96 hours prior to dosing until discharge from the CRU at the end of the study.

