1.2.1.2 Safety

To date, balovaptan has been found to be safe and well tolerated in clinical trials. No particular safety concerns have emerged, and no adverse drug reactions have been identified. More specifically, creatine phosphokinase (CPK) was monitored in previous trials based on observations of muscle toxicity in rats; no changes of any importance were noticed. Similarly, no hematology or neurotoxicity findings have been observed in clinical trials. The maximum tolerated dose was not reached in either the single ascending dose (SAD) study with single doses (up to 76 mg) or the multiple ascending dose (MAD) study with multiple doses (up to 52 mg qd for 14 days) in healthy subjects. In light of convulsions observed in dogs, dose escalation was stopped so as not to exceed a C_{max} (mean) of 810 ng/mL in the SAD and MAD studies. In healthy volunteer studies, one serious adverse event (SAE) of bacterial infection (suspected Lyme disease) was reported in Study BP29412; this SAE was considered unrelated to study drug.

Balovaptan has also been found to be safe and well tolerated in male patients with ASD at doses up to 10 mg/day (highest dose administered) for a period of 12 weeks (Study BP28420). No particular safety patterns attributable to the administration of balovaptan were identified. A total of 8 SAEs (all but one [rhabdomyolysis] considered unrelated to study drug) in 4 patients and 1 adverse event (AE) of special interest (neutropenia) were reported in the study. No relevant safety concern has emerged from the recently started study in ASD pediatric patients (BP30153).

Based on the review of all available data, it is currently recommended not to exceed a plasma exposure equivalent to 20 mg qd in adult subjects in clinical trials with a continuous treatment duration longer than 4 weeks.

Refer to the Investigator's Brochure for details on nonclinical and clinical studies.

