3. STUDY DESIGN

3.1 DESCRIPTION OF THE STUDY

This study will be a single-center, non-randomized, open-label, one-sequence, two-period within-subject study to investigate the effects of multiple doses of rifampicin on the PK and safety of multiple doses of balovaptan in healthy subjects. The study will be conducted at 1 site in the Netherlands.

Screening will be conducted up to 3 weeks prior to admission to the clinical research unit (CRU). Subjects will be in the CRU for 2 study periods. In both periods, subjects will be admitted on Day -1 (the day before dosing begins); Day 1 will be the first day of dosing. In Period 1, subjects will be discharged on Day 11 after the last assessment is

completed. There will be a minimum of a 14-day to a maximum of a 21-day washout between the last dose in Period 1 and the first dose in Period 2. Subjects will therefore return to the CRU on Day 24 or up to Day 30 of Period 1 (Day -1 of Period 2) to begin Period 2. Day 1 will be the first day of dosing. In Period 2, subjects will be discharged on Day 17 after all assessments have been performed. Subjects will return for a follow-up visit between 14 to 21 days after the last dose.

Subjects will receive the following study drugs in the 2 study periods after an overnight fast of at least 8 hours:

Period 1:

[figure not shown]
- Days 1 to 10: oral balovaptan 10 mg qd
- Days 11 to 23 (or up to Day 30): no study drug

Period 2:

- Days 1 to 6: rifampicin 600 mg qd
- Days 7 to 16: balovaptan 10 mg qd + rifampicin 600 mg qd

Figure 1 presents an overview of the study design. A schedule of activities is provided in Appendix 1.

Figure 1 Study Schema

Abbreviations: PK = pharmacokinetic; qd = once daily;

^aFull balovaptan PK profile on Day 10/11 of Period 1 and Day 16/17 of Period 2; trough concentrations on other days. Full rifampicin PK profile on Days 6/7 and 16/17 of Period 2

Subjects will undergo study assessments and procedures as detailed in the schedule of assessments (Appendix 1), including assessments of AEs and concomitant medications,

vital signs, 12-lead ECGs, clinical laboratory evaluations and blood sampling for PK assessments.

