5.2.3 Adverse Events of Special Interest (Immediately Reportable to the Sponsor)

Adverse events of special interest are required to be reported by the Investigator to the Sponsor immediately (i.e., no more than 24 hours after learning of the event; see Section 5.4.2 for reporting instructions). Adverse events of special interest for this study are as follows:

- Cases of potential drug-induced liver injury that include an elevated ALT or AST in combination with either an elevated bilirubin or clinical jaundice, as defined by Hy's Law (see Section 5.3.5.6)
- Suspected transmission of an infectious agent by the study drug, as defined below
Any organism, virus, or infectious particle (e.g., prion protein transmitting transmissible spongiform encephalopathy), pathogenic or non-pathogenic, is considered an infectious agent. A transmission of an infectious agent may be suspected from clinical symptoms or laboratory findings that indicate an infection in a subject exposed to a medicinal product. This term applies only when a contamination of the study drug is suspected.
- Clinically relevant decreases in ANC and for which no alternative explanation has been identified (i.e., the relationship to study drug is rated "yes").

- CPK values that exceed 10× ULN for several days without a trend of normalization or are associated with relevant dysfunction of kidneys, and if no alternative explanation exists.
- Neurological abnormalities emerging from AE reporting or neurologic examination that are potentially indicative of dysfunction of peripheral nerves or otherwise represent a neurological deficit and for which no other explanation is apparent
- Adverse events such as: arrhythmia, syncope, dyspnea, palpitations, or chest pain

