- j Hematology and chemistry at Screening and on Days -1 and 11 of Period 1 and on Days -1, 3, 6, 9, 13, 17 in Period 2, and follow up. Urinalysis at Screening and on Days -1 and 11 of Period 1 and on Days -1 and 17 in Period 2 and at Follow-up.
- k For females only: FSH and serum pregnancy test at Screening, and serum pregnancy test only at all other time points.
- l Subjects will be admitted to the clinical research unit on Day -1 of Period 1 and Period 2 and will be discharged on Day 11 and Day 17 of Period 1 and 2, respectively, after completion of study assessments.

Appendix 2

Schedule of Pharmacokinetic Samples and Electrocardiogram, and Vital Signs Measurements

Procedure Study Day	Predose or Prior to Admission/Discharge	Hours post dose ^a												
		0.5	1	1.5	2	2.5	3	4	6	8	12	16	24	
Blood sampling balovaptan, M2, and M3 (one sample for all 3 analytes)														
Period 1														
Days 2, 4, 8, and 9	X ^b													
Day 10	X ^b	X	X	X	X	X	X	X	X	X	X	X	X ^c	X ^c
Period 2														
Days 8, 10, 14, and 15	X ^b													
Day 16	X ^b	X	X	X	X	X	X	X	X	X	X	X	X ^d	X ^d
Blood sampling rifampicin														
Period 2														
Day 6	X ^b		X	X	X		X	X	X		X		X ^e	
Day 16	X ^b		X	X	X		X	X	X		X		X ^d	
12-lead electrocardiograms														
Period 1														
Day -1 and Day 11	X ^f													
Days 3, 7, and 10	X ^b						X							
Period 2														
Day -1 and Day 17	X ^f													
Days 3, 6, 9, 13, and 16	X ^b						X							
Vital signs														
Period 1														
Day -1 and Day 11	X ^f													
Days 3, 7, and 10	X ^b						X							
Period 2														
Day -1 and Day 17	X ^f													
Days 3, 6, 9, 13, and 16	X ^b						X							

Appendix 2

Schedule of Pharmacokinetic Samples and Electrocardiogram, and Vital Signs Measurements (cont.)

^aFor sampling to measure balovaptan, M2, and M3, and for ECG and vital signs measurements on days balovaptan or balovaptan together with rifampicin are administered, post dose is relative to time of balovaptan dosing; for sampling to measure rifampicin and for ECG and vital signs measurements on days balovaptan is not administered, post dose is relative to time of rifampicin dosing

^b10 minutes predose (or time matched, when not dosed)

^cDay 11

^dDay 17

^eDay 7

^fPrior to admission or discharge

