### Appendix 2: Schedule of Assessments

Assessments	Washout of minimally 14 and maximally 21 days between the study periods													
	Screening	Period 1					Period 2							Follow-up
	Day -21 to Day -2	Day -1	Days 1-9	Day 10	Day 11	Washout: for 14-21 days after last dose	Day -1	Days 1-5	Day 6	Day 7	Days 8-15	Day 16	Day 17	Days 30 – 37 of Period 2
Written informed consent	X													
Inclusion and exclusion criteria	X													
Demographics	X													
Medical history	X													
Medication history	X													
Study drug administration: balovaptan a			X	X					X	X	X			
Study drug administration: rifampicin a								X	X	X	X	X		
Standardized meals b				X					X			X		
Pharmacokinetic sampling balovaptan c			X	X	X						X	X	X	
Clinical genotyping sample		X												
Pharmacokinetic sampling rifampicin d									X	X		X	X	
Physical examination	X e				X		X f						X	X f
Triplicate 12-lead ECG g	X	X	X	X	X		X	X	X	X	X	X	X	X
Vital signs h	X i	X i	X	X i	X i		X i	X	X	X	X	X i	X i	X i
Hematology j	X	X			X		X	X	X	X	X		X	X
Serum chemistry j	X	X			X		X	X	X	X			X	X
Urinalysis j	X	X			X		X						X	X
Coagulation	X						X							
Urine drug screen	X	X					X							
Urine alcohol test	X	X					X							
Serology	X													
Pregnancy test k	X	X					X							X
Resident at study center l		X	X	X	X		X	X	X	X	X	X	X	
Adverse event monitoring	X	←—————→					←—————→							X
Review concomitant medications	X	←—————→					←—————→							X
C-SSRS	X				X								X	

Abbreviations: BMI = body mass index; C-SSRS= Columbia Suicide Severity Rating Scale; ECG = electrocardiogram; qd = once daily;

- 
- a Study drugs will be administered after an overnight fast of at least 8 hours, 30 minutes prior to breakfast. On days rifampicin and balovaptan are coadministered, they will be administered at the same time. Water will be allowed ad libitum up to 1 hour prior to dosing and from 1 hour post dosing, and no food is allowed for at least 4 hours post dose—lunch, dinner, and afternoon/ evening snacks will be provided 4 or more hours after dosing.

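### The exercise restriction stops at Day 17 discharge, leaving the follow-up CPK as the only one of eight panels after first dosing taken without exercise control.

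*Protocol*

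**What the plan says.** The exercise rule is in Protocol Section 4.4.4: "Subjects should refrain from strenuous exercise for at least 96 hours prior to dosing until discharge from the CRU at the end of the study". Section 3.1 fixes the end of that window: in Period 2, "subjects will be discharged on Day 17 after all assessments have been performed". The last dosing block is "Days 7 to 16: balovaptan 10 mg qd + rifampicin 600 mg qd", and "Subjects will return for a follow-up visit between 14 to 21 days after the last dose". SAP Appendix 2 gives the visit as "Days 30 – 37 of Period 2".

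CPK is listed in the blood chemistry panel (Protocol Section 4.5.5.1). Footnote j of Protocol Appendix 1 schedules chemistry at Screening, on Days -1 and 11 of Period 1, and on "Days -1, 3, 6, 9, 13, 17 in Period 2, and follow up".

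Muscle safety is a declared interest. Section 1.2.1.2 says CPK was monitored in earlier trials because of muscle toxicity in rats, and that no changes of importance were seen. For the adult patient study it reports: "A total of 8 SAEs (all but one [rhabdomyolysis] considered unrelated to study drug". Section 5.2.3 makes an event of special interest of "CPK values that exceed 10× ULN for several days without a trend of normalization", or of values that come with relevant kidney dysfunction, and in either case only where nothing else explains them.

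Other rules in Section 4.4.4 do reach follow-up. The pre-visit fast names that visit, and the alcohol limit runs through to it.

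**The concern.** Strenuous exercise is a competing cause of a raised CPK. The protocol recognises this by restricting exercise around dosing, but the restriction lapses before the last CPK sample. The readable text does not ask for an exercise history at that visit, and Section 5.3.2 prescribes non-directive questions about adverse events, so the investigator may not learn of recent exercise.

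The consequence would follow from the ordinary adverse event rules:

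- Section 5.3.5.4 makes a laboratory value an adverse event if the investigator judges it clinically significant.
- Section 5.3.1 keeps the reporting period open until 21 days after the last dose, which includes the follow-up visit.
- Table 3 in Section 5.3.4 treats an event as related unless there is evidence of another cause or no plausible timing.
- SAP Section 17.1.1 attributes an event to the last treatment received, here balovaptan plus rifampicin.

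At stake is the reading of one late safety value per subject, and possibly some repeat testing.

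**Working it through.** **1. Follow-up window (reproducing the plan's figure).** The last dose is on Day 16 of Period 2 and follow-up is 14 to 21 days later (Protocol Section 3.1).

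- 16 + 14 = Day 30
- 16 + 21 = Day 37

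This matches SAP Appendix 2.

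**2. Days without the restriction before the follow-up sample.** Discharge is on Day 17.

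- 30 − 17 = 13 days
- 37 − 17 = 20 days

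**3. CPK panels after first dosing (footnote j).**

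| Panel | Exercise restricted? |
|---|---|
| Period 1 Day 11 | yes |
| Period 2 Day -1 | yes |
| Period 2 Days 3, 6, 9, 13, 17 | yes (five panels) |
| Follow-up, Days 30 to 37 | no |

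The total is 1 + 1 + 5 + 1 = 8, of which one is unrestricted.

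Period 2 Day -1 counts as restricted on either reading of Section 4.4.4. If the rule runs continuously to final discharge, it covers the washout. If it restarts 96 hours before dosing in each period, Day -1 (about 24 hours before dosing) comes after roughly 96 − 24 = 72 hours of restriction.

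**4. Which panels are late.** The first Period 2 dose is 14 to 21 days after the last Period 1 dose, so Day -1 falls about 13 to 20 days after it. That is close to the 14 to 21 days at follow-up. Period 2 Day -1 is therefore a late, exercise-restricted sample after balovaptan alone. Follow-up is the only late sample after the combination. Day 17 is also after the last combination dose, but only by one day.

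**5. Balovaptan left at follow-up.** Section 1.2.1.1 gives a half-life of about 46 hours after repeated dosing. The remaining fraction is 0.5^(hours/46).

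- 14 days: 336/46 = 7.3 half-lives, remaining fraction 0.0063, about 0.6%
- 21 days: 504/46 = 11.0 half-lives, remaining fraction 0.0005, about 0.05%

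This assumes simple exponential decline and applies to the parent drug only. The 46-hour figure comes from dosing without rifampicin. The documents give no half-life for M2 or M3.

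**6. Screening.** SAP Section 9.2.1 takes the last observation before first dosing in each period as baseline. Chemistry is scheduled on Period 1 Day -1, inside the 96-hour restriction. Exclusion criterion 15 in Section 4.1.2 also allows questionable screening results to be repeated on Day -1 (the synopsis says before Day -1). An exercise-related screening value therefore need not reach the baseline.

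**The case against.** The strongest case against runs as follows.

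- **The event definition already guards against this.** It needs values above 10 times the upper limit for several days without normalising, or kidney dysfunction, and no other explanation. One follow-up value cannot show several days, and exercise would be another explanation. This stands: a reader might infer that a post-exercise CPK at follow-up becomes an event of special interest, but Section 5.2.3 does not support that. What remains is that the exclusion of other explanations works only if the exercise is known about.
- **The plan can already resolve an odd value.** Section 4.5.5.1 allows extra samples for out-of-range results, Section 5.3.4 tells the investigator to weigh other causes, and Section 5.3.5.4 leaves isolated abnormalities to judgment. This also stands. It limits the harm to avoidable retesting or a doubtful attribution.
- **Late drug-related toxicity is unlikely with so little drug left.** This is fair, but it cuts both ways: a late rise is then more likely to have an outside cause, which is a reason to control or record exercise.
- **Ending the rule at final discharge is a coherent choice.** The tobacco ban and the ban on CYP3A-modulating foods also end at discharge. No two passages contradict each other, so this is an improvement and not the correction of an error.
- **The muscle-toxicity text is redacted.** Sections 5.1.1.2 and 5.1.2.3 appear in the contents but cannot be read. They may contain exercise guidance, so its absence from the plan cannot be claimed.

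A reader might also infer that follow-up is the only panel able to show a delayed muscle effect. The documents do not support that, because Period 2 Day -1 gives a restricted late sample after ten days of balovaptan alone.

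**Conclusion.** The point holds in a limited form. One of eight CPK panels after first dosing is taken without exercise control, 13 to 20 days after the restriction ends, and it is the only late panel after the combination period. The realistic consequence is a rise below the special-interest definition that is reported as a related adverse event under the combination, or is retested needlessly.

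The size of any exercise-related rise is not in the documents, so the number of subjects affected cannot be estimated. The conclusion assumes that the redacted skeletal-muscle sections do not already cover exercise before follow-up. The primary PK endpoints and their analysis are unaffected, and nothing here suggests that the muscle-safety monitoring as a whole is unsound. This is a cheap improvement, not a defect that threatens the study.

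**What to change.** Extend the exercise sentence in Protocol Section 4.4.4 with a closing clause: '... and for 96 hours before the follow-up visit'. Repeat it in the subject instructions. If Section 5.1.1.2 or 5.1.2.3 already contains such guidance, a cross-reference is enough. No extension to screening is needed.

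The cost is one clause and about four more days of restricted exercise per subject. Subjects would still have 9 to 16 unrestricted days after discharge (13 − 4 and 20 − 4). No visit, sample or procedure is added, and the SAP needs no change.
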